2.3 Benefit/Risk Assessment

Pembrolizumab monotherapy has shown significant activity in the setting of dMMR/MSI-H mCRC in both first line and later settings. However, the benefit is not universal; in the KEYNOTE-177 study approximately 40% of participants showed disease progression soon after beginning treatment.

The addition of a CTLA-4 antibody (ie, ipilimumab), in an uncontrolled dMMR/MSI-H cohort, has appeared to increase the effectiveness of immunotherapeutic approaches against these tumors. Participants with dMMR/MSI-H CRC treated with both CTLA-4 and PD-1 inhibition had a response rate of 62% and 12-month PFS of 76% [Lenz, H. J., et al 2020] whereas pembrolizumab monotherapy had a response rate of 44% and 12-month PFS of 55% [Andre, T., et al 2020]. However, these approaches have never been directly compared, which is the goal of this study.

The existing preclinical and early clinical data suggest that inhibiting other immune checkpoint molecules in combination with PD-1 blockade is a promising therapeutic strategy and that the risk/benefit assessment for participants in this study will be favorable.

Phase 1 studies have shown that MK-4830 and MK-7684 as monotherapy or in combination with pembrolizumab can potentially enhance antitumor efficacy in patients with solid tumors (refer to respective IBs and Section 2.1). Also, preliminary results support the use of MK-1308 and MK-4280 in combination with pembrolizumab (refer to respective IBs and Section 2.1). An advantage of the platform study design is that it will allow rapid, concurrent evaluation of multiple investigational agents in chemotherapy refractory and previously untreated participants with metastatic dMMR/MSI-H CRC. This may identify new combination interventions with improved responses over those historically achieved with current treatment options. Therefore, a potential benefit may be faster clinical development of novel interventions benefiting this particular patient population, while reducing exposure of participants to interventions that do not show improved clinical benefit. Nevertheless, combination therapy might prove to have greater toxicity rates, particularly with respect to colitis and hepatitis. A goal of this study will be to formally assess AE and SAE rates.

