6.1.1 Treatment

6.1.1.1 Initial Treatment or First Course

The Initial Treatment or First Course of MK-1308A or pembrolizumab monotherapy consists of up to 17 treatments of Q6W therapy. The Initial Treatment or First Course of MK-4280A, MK-7684A, or MK-4830 plus pembrolizumab consists of up to 35 treatment cycles of Q3W therapy. Note: The number of treatments is calculated starting with the first dose.

Participants may be eligible for Second Course described in Section 6.1.1.2.

In the event of a study arm being closed, the Sponsor may offer investigators the option of continuing study treatment with pembrolizumab monotherapy or continuing the assigned study treatment to participants who are receiving clinical benefit. At implementation of Amendment 05, the following treatment arms are considered closed: Cohort B: MK-4280A, Cohort B: MK-7684A, and Cohort B: MK-4830+pembrolizumab.

As of the Investigator Letter dated 16-DEC-2024, participants who were receiving MK-4280A were offered the option to continue study therapy until treatment completion or transition to pembrolizumab monotherapy, and participants who were receiving MK-7684A were discontinued from that study therapy and offered the option to transition to pembrolizumab monotherapy. As per the Investigator Letter dated 25-SEP-2023, the MK-4830+pembrolizumab arm was closed to enrollment; all ongoing participants were offered the option to continue study therapy until treatment completion or transition to pembrolizumab monotherapy. For participants who elect to transition to pembrolizumab monotherapy, the dosage would be 200 mg Q3W up to a total of 35 doses including doses received as part of closed arm.

Participants in closed arms with access to approved SOC (eg, immunotherapy, chemotherapy, targeted therapy) should be considered for discontinuation from the study. Participants in closed arms who are benefiting from pembrolizumab monotherapy, but unable to access it as SOC outside the study, may continue on study and receive treatment with pembrolizumab monotherapy until discontinuation criteria are met. The final required study visit will be the Safety Follow-up Visit.

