8.4 Adverse Events, Serious Adverse Events, and Other Reportable Safety Events

The definitions of an AE or SAE, as well as the method of recording, evaluating, and assessing causality of AE and SAE and the procedures for completing and transmitting AE, SAE, and other reportable safety event reports can be found in Appendix 3.

Progression of the cancer under study is not considered an AE as described in Section 8.4.6 and Appendix 3.

Adverse events, SAEs, and other reportable safety events will be reported by the participant (or, when appropriate, by a caregiver, surrogate, or the participant's legally authorized representative).

The investigator and any designees are responsible for detecting, documenting, and reporting events that meet the definition of an AE or SAE as well as other reportable safety events. Investigators need to document if an SAE was associated with a medication error, misuse, or abuse.

Investigators remain responsible for following up AEs, SAEs, and other reportable safety events for outcome according to Section 8.4.3. The investigator, who is a qualified physician, will assess events that meet the definition of an AE or SAE as well as other reportable safety events with respect to seriousness, intensity/toxicity, and causality.

8.4.1 Time Period and Frequency for Collecting AE, SAE, and Other Reportable Safety Event Information

All AEs, SAEs, and other reportable safety events that occur after the participant provides documented informed consent, but before intervention allocation, must be reported by the investigator if the participant is receiving placebo run-in or other run-in treatment, if the event causes the participant to be excluded from the study, or is the result of a protocol-specified intervention, including, but not limited to washout or discontinuation of usual therapy, diet, or a procedure.

- All AEs from the time of intervention allocation through 30 days after cessation of study intervention must be reported by the investigator.
- All AEs meeting serious criteria, from the time of intervention allocation through 90 days after cessation of study intervention or 30 days after cessation of study intervention if the participant initiates new anticancer therapy, whichever is earlier, must be reported by the investigator.

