9.6.2 Statistical Methods for Safety Analyses

Safety and tolerability will be assessed by clinical review of all relevant parameters including AEs, laboratory tests and vital signs. Safety analyses will be conducted for each cohort separately.

The analysis of safety results will follow a tiered approach ([Table 12](#)). The tiers differ with respect to the analyses that will be performed. AEs (specific terms as well as system organ class terms) and events that meet predefined limits of change in laboratory and vital signs are either prespecified as “Tier 1” endpoints or will be classified as belonging to “Tier 2” or “Tier 3” based on observed proportions of participants with an event.

Tier 1 Events

CCI

CCI

Tier 2 Events

Tier 2 parameters will be assessed via point estimates with 95% CIs provided for differences in the proportion of participants with events using the M&N method, an unconditional, asymptotic method [Miettinen, O. and Nurminen, M. 1985].

Membership in Tier 2 requires that at least 10% of participants in any treatment group exhibit the event; all other AEs and predefined limits of change will belong to Tier 3. The threshold of at least 10% of participants was chosen for Tier 2 events because the population enrolled in this study is in critical condition and usually experiences various AEs of similar types regardless of treatment; events reported less frequently than 10% of participants would obscure the assessment of the overall safety profile and add little to the interpretation of potentially meaningful treatment differences. In addition, Grade 3 to 5 AEs ($\geq 5\%$ of participants in 1 of the treatment groups) and SAEs ($\geq 5\%$ of participants in 1 of the treatment groups) will be considered Tier 2 endpoints. Because many 95% CIs may be provided without adjustment for multiplicity, the CIs should be regarded as a helpful descriptive measure to be used in safety review, not as a formal method for assessing the statistical significance of the between-group differences.

Tier 3 Events

Safety endpoints that are not Tier 1 or 2 events are considered Tier 3 events. The broad AE categories consisting of the proportion of participants with any AE, a drug-related AE, a serious AE, an AE which is both drug-related and serious, a Grade 3-5 AE, a drug-related Grade 3-5 AE, and discontinuation due to an AE will be considered Tier 3 endpoints. Only point estimates by treatment group are provided for Tier 3 safety parameters.

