9.12 Extent of Exposure

Extent of exposure for a participant is defined as the number of cycles and number of days for which the participant receives the study intervention for each cohort. Summary statistics will be provided on the extent of exposure for the APaT population.

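### In the legible plan, adverse events are compared between arms as crude proportions, which cannot separate toxicity from time at risk, above all in the three closed Cohort B arms

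*Combined protocol and SAP*

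**What the plan says.** Section 9.6.2 sorts safety endpoints into tiers. For Tier 2, "Tier 2 parameters will be assessed via point estimates with 95% CIs provided for differences in the proportion of participants with events using the M&N" approach. An event enters Tier 2 when at least 10% of any arm has it, or 5% for Grade 3 to 5 and serious AEs. The broad Tier 3 categories include any AE, serious AE, Grade 3-5 AE and discontinuation due to an AE; there, "Only point estimates by treatment group are provided for Tier 3 safety parameters". On the Tier 2 intervals the section adds that "the CIs should be regarded as a helpful descriptive measure to be used in safety review, not as a formal method" of judging significance.

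Section 8.4.1 sets the collection window. "All AEs from the time of intervention allocation through 30 days after cessation of study intervention must be reported by the investigator". Serious AEs run "through 90 days after cessation of study intervention or 30 days after cessation of study intervention if the participant initiates new anticancer therapy"; the earlier of the two limits applies. Under Section 4.1, treatment lasts about two years or until a discontinuation criterion is met.

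Sections 4.1 and 6.1.1.1 describe three closed Cohort B arms. MK-7684A was stopped, with a move to pembrolizumab monotherapy on offer. MK-4280A and MK-4830+pembrolizumab participants could continue or switch. In addition, "Participants in closed arms with access to approved SOC (eg, immunotherapy, chemotherapy, targeted therapy) should be considered for discontinuation from the study".

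Section 9.5.2 keeps participants in their randomized group for safety unless they took the wrong treatment throughout. Section 9.12 states that "Extent of exposure for a participant is defined as the number of cycles and number of days for which the participant receives the study intervention", summarized descriptively. The legible text does not connect it to the AE results.

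**The concern.** A proportion of participants with an event grows with the time over which events are collected. Here that time is time on treatment plus a short tail, so two arms with the same toxicity per month can show different proportions if one is treated longer.

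Two mechanisms could produce this:

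- **Outcome.** In every comparison, treatment length responds to efficacy and to stopping for toxicity.
- **Closure.** In three Cohort B arms a sponsor decision ended or changed treatment. Under Section 9.5.2, AEs arising on monotherapy after a switch still count toward the original combination. No legible rule covers these AEs or those of Second Course.

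Section 2.3 makes assessment of AE and serious AE rates a goal and names colitis and hepatitis. A difference that mixes toxicity with time at risk, and in closed arms with a sponsor decision, is hard to use for that goal. The crude proportion also decides which events reach Tier 2, so unequal exposure can determine whether an event gets a between-arm interval at all.

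**Working it through.** **What can be checked directly.** 17 doses × 6 weeks = 102 weeks and 35 × 3 weeks = 105 weeks, both about two years as stated. Counting from first dose, a full course closes the AE window at day 16 × 42 + 30 = 702 (Q6W) and at day 34 × 21 + 30 = 744 (Q3W). The windows therefore differ by 42 days by design. The plan gives no legible figure for the size of the exposure effect, so what follows is an illustration.

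**Inputs from the documents.** Section 2.3 gives 12-month PFS of 55% for pembrolizumab. For an external, uncontrolled CTLA-4 plus PD-1 cohort it says participants "had a response rate of 62% and 12-month PFS of 76" per cent. Section 2.1 gives 22% Grade 3+ events on pembrolizumab.

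**Assumptions.** Time on treatment is exponential with the PFS hazard, capped at 24 months. The AE window adds 30 days (0.986 month). The AE hazard is identical in both arms and set to give 22% on pembrolizumab.

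**Time at risk.** λ = −ln(PFS)/12 gives 0.04982 and 0.02287 per month. Mean treatment time (1 − e^(−24λ))/λ is 14.0 and 18.5 months (1.17 and 1.54 years, ratio 1.32). Mean AE windows are 15.0 and 19.5 months.

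**Crude proportion, constant AE hazard h.**

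P = 1 − e^(−0.986h) × [λ/(λ+h) × (1 − e^(−24(λ+h))) + e^(−24(λ+h))]

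Setting P = 0.22 on pembrolizumab gives h = 0.01733.

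- Pembrolizumab: 1 − 0.9831 × (0.7419 × 0.8004 + 0.1996) = 22.0%.
- Longer-treated arm: 1 − 0.9831 × (0.5689 × 0.6189 + 0.3811) = 27.9%.

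Person-time to first event is P/h = 12.70 and 16.11 months. The rate is 1.73 per 100 person-months in both arms, as it must be.

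**Other hazard shapes, each recalibrated to 22%, by numerical integration.**

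| AE hazard | Longer-treated arm | Excess (points) |
|---|---|---|
| Constant | 27.9% | +5.9 |
| Weibull, shape 0.7 | 26.4% | +4.4 |
| Weibull, shape 0.5 | 25.3% | +3.3 |
| Falls to one quarter after 3 months | 25.8% | +3.8 |
| Falls to one tenth after 3 months | 24.4% | +2.4 |

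**More stopping for toxicity on the combination.** An assumed extra 10% per year cuts the excess, over the constant and the two falling hazards, to 1.5–3.7 points. At 20% per year it is 0.6–1.6 points.

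**Closure.** Suppose treatment is cut at a fixed time with no switch, efficacy equals control, and the AE hazard is the same.

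| AE hazard | Cut at 6 months | Cut at 12 months |
|---|---|---|
| Constant | 10.1% (−11.9) | 15.7% (−6.3) |
| Weibull, shape 0.7 | 13.2% (−8.8) | 17.7% (−4.3) |
| Weibull, shape 0.5 | 15.5% (−6.5) | 19.0% (−3.0) |

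The shortfall shrinks as events become more front-loaded. Under a constant hazard, a true AE hazard ratio of 1.5 with a 12-month cut shows 22.5% against 22.0%, so it is almost hidden. With front-loaded events the masking is less complete.

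**Scale.** Arm sizes are redacted. For an assumed 40 to 60 per arm (320/7 ≈ 46), the half-width 1.96 × √(2 × 0.22 × 0.78/n) is 18 to 15 points.

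**The case against.** Much of the opposing case stands.

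- **Redaction.** Tier 1, Table 12, the interim section and part of the Section 9 introduction are blacked out. The summary of changes says Amendment 05 added future analysis plans to Section 9. A reader might infer that crude proportions are the only comparison planned; that cannot be established.
- **Estimand.** A reader might call the difference confounded. Exposure follows from randomized treatment, so the crude difference is a valid estimate of risk under the regimen as given. Toxicity per unit time is a different question.
- **MK-1308A.** A reader might infer that the protocol expects 76% PFS and that MK-1308A will look more toxic because it works. The 76% comes from an external first-line cohort given ipilimumab with nivolumab. Section 2.3 says the approaches have never been directly compared. Cohort A is chemotherapy refractory, where Section 2.1 reports median PFS of 2.3 to 4.1 months on pembrolizumab. Time on treatment also departs from PFS: participants may continue beyond progression, stop after complete response, or stop for toxicity.
- **Closure.** A reader might infer that all closed arms were stopped. Only MK-7684A was. Switchers may continue to 35 total doses, and monitoring runs through the AE reporting period. Closure touches no Cohort A arm and not MK-1308A against pembrolizumab in Cohort B.
- **Size.** The illustrated effects are smaller than the likely interval half-width, and the intervals are declared descriptive. They are nonetheless systematic, and the interval does not reflect them.
- **Remedy.** Person-time rates mislead for front-loaded events. Truncating only the closed arms would keep their early, higher-hazard time against full pembrolizumab follow-up. The fix has to handle both.

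None of this supplies a legible analysis that separates toxicity from time at risk, or a rule for post-switch and Second Course AEs.

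**Conclusion.** The point holds as a moderate gap in interpretability that is cheap to close. In the legible text, the between-arm AE comparison is a crude difference in proportions over a window that follows the last dose, and the exposure summary is not linked to it.

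The gap matters most for MK-4280A, MK-7684A and MK-4830+pembrolizumab, where sponsor decisions altered treatment and monotherapy AEs after a switch stay with the original arm. For MK-1308A against pembrolizumab in either cohort, only differential efficacy or stopping for toxicity can separate exposure. The sign is unknown, so the documents do not support a claim that the plan will overstate its toxicity.

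The sizes are illustrative: about +2 to +6 points from longer treatment, less if the combination is stopped more often for toxicity, and about −3 to −12 points from closure. They rest on PFS standing in for time on treatment, assumed AE hazard shapes, a 22% base rate and assumed closure times. The closure figures treat every participant as cut at the same time without switching. The number still on treatment at closure is not visible, and anyone who had already finished would dilute the arm-level effect.

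**What to change.** Keep the crude proportions. In Section 9.6.2 or the supplemental SAP, add for Tier 2 events and for Grade 3-5, serious and discontinuation AEs:

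1. Cumulative incidence of first event over a fixed early window common to all arms, with end of treatment and death as competing events.
2. Exposure-adjusted incidence rates over the AE collection window, with a 95% CI for the difference from pembrolizumab, read beside item 1 because rates mislead when events are front-loaded.
3. For the closed arms, results truncated at the closure or switch date, with the same calendar or time truncation applied to concurrently randomized pembrolizumab participants.
4. AEs after a switch to monotherapy and AEs in Second Course shown separately, with the counting rule stated.

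If the redacted text already provides any of these, a cross-reference from Section 9.6.2 is enough. Dosing dates (Section 6.4) and AE reports (Section 8.4.1) are already collected, so no new data are needed and treatment is unaffected. The cost is more safety tables and some programming.

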Objective (Cohort B): To compare MK-1308A, MK-4280A, MK-7684A, MK-4830+Pembrolizumab, and pembrolizumab monotherapy with respect to Progression-Free Survival per RECIST 1.1 as assessed by the investigator	Progression-Free Survival: The time from randomization to the first documented disease progression or death due to any cause, whichever occurs first
Objective (Cohort A): To compare MK-1308A and pembrolizumab monotherapy with respect to Objective Response Rate per RECIST 1.1 as assessed by the investigator	Objective Response: Complete Response or Partial Response
Objective (Cohort B): To compare MK-1308A, MK-4280A, MK-7684A, MK-4830+Pembrolizumab, and pembrolizumab monotherapy with respect to Objective Response Rate per RECIST 1.1 as assessed by the investigator	Objective Response: Complete Response or Partial Response
Objective (Cohort A and B): To evaluate Duration of Response per RECIST 1.1 as assessed by the investigator	The time from first documented evidence of Complete Response or Partial Response until disease progression or death due to any cause, whichever occurs first
Objective (Cohort A): To compare MK-1308A and pembrolizumab monotherapy with respect to Overall Survival	Overall Survival: The time from randomization to death due to any cause
Objective (Cohort B): To compare MK-1308A, MK-4280A, MK-7684A, MK-4830+Pembrolizumab, and pembrolizumab monotherapy with respect to Overall Survival	Overall Survival: The time from randomization to death due to any cause
Objective (Cohort A): To evaluate the safety and tolerability of MK-1308A compared to pembrolizumab monotherapy	Adverse Events Study intervention discontinuation due to Adverse Events

Objective (Cohort B): To evaluate the safety and tolerability of MK-1308A, MK-4280A, MK-7684A, MK-4830+Pembrolizumab, and compared to pembrolizumab monotherapy	Adverse Events Study intervention discontinuation due to Adverse Events
Tertiary/Exploratory Objectives	Tertiary/Exploratory Endpoints

CCI
 

	

CCI

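### Discontinuation due to an AE and the overall AE proportions get per-arm point estimates only, although the safety objective is worded as a comparison with pembrolizumab monotherapy

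*Combined protocol and SAP*

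**What the plan says.** **Objective and endpoints (Section 3).** For Cohort A the safety objective reads "To evaluate the safety and tolerability of MK-1308A compared to pembrolizumab monotherapy". For Cohort B it reads "To evaluate the safety and tolerability of MK-1308A, MK-4280A, MK-7684A, MK-4830+Pembrolizumab, and compared to pembrolizumab monotherapy". Both list the same two endpoints: "Adverse Events Study intervention discontinuation due to Adverse Events".

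**Stated goal (Section 2.3).** After noting that combinations may prove more toxic, particularly for colitis and hepatitis, the protocol adds: "A goal of this study will be to formally assess AE and SAE rates".

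**Safety tiers (Section 9.6.2).**
- Tier 2 events get a between-arm difference in proportions with an M&N 95% CI. Tier 2 covers AE terms and predefined laboratory or vital-sign changes seen in at least 10% of any arm, plus Grade 3 to 5 AEs and SAEs seen in at least 5% of one arm. The section calls these intervals descriptive and unadjusted for multiplicity.
- Tier 3 includes, by name, "The broad AE categories consisting of the proportion of participants with any AE, a drug-related AE, a serious AE", a drug-related serious AE, a Grade 3-5 AE, "a drug-related Grade 3-5 AE, and discontinuation due to an AE will be considered Tier 3 endpoints".
- For that tier, "Only point estimates by treatment group are provided for Tier 3 safety parameters".

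The Tier 1 text and the body of Table 12 are redacted.

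**The concern.** Discontinuation due to an AE is a named secondary endpoint under an objective worded as a comparison with the control arm. The analysis assigned to it describes each arm separately and never estimates the contrast. The assignment is by name, so it holds however often the event occurs, even where the rate would pass the 10% threshold that brings an ordinary AE term into Tier 2. The overall AE proportions are treated in the same way.

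At stake is how the overall tolerability cost of adding a second checkpoint inhibitor will be read. In small arms two percentages side by side can look like a clear difference, or like none, and nothing in the planned output for these measures shows how imprecise the contrast is. A difference worked out afterwards from reported counts would not be prespecified.

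**Working it through.** The plan states no figure on this point, so there is none to reproduce. The check has a textual part and an illustrative one.

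**1. Endpoints against planned analyses**

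| Measure | Status in Section 3 | Tier in 9.6.2 | Between-arm difference and CI planned? |
|---|---|---|---|
| Discontinuation due to an AE | Named secondary endpoint | 3, by name | No |
| Overall proportions: any, drug-related, serious, drug-related serious, Grade 3-5, drug-related Grade 3-5 AE | Not listed singly; the endpoint is adverse events in general | 3, by name | No |
| AE terms at 10% or more in any arm | Within adverse events | 2 | Yes, M&N |
| Grade 3-5 AEs and SAEs at 5% or more in one arm | Within adverse events | 2 | Yes, M&N |

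One wording problem shows up here. Grade 3-5 AEs and SAEs appear in Tier 2, while a Grade 3-5 AE and a serious AE appear in Tier 3. The two agree only if the Tier 2 sentence means specific terms and the Tier 3 sentence means the overall proportions. The Tier 2 sentence does not say so.

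**2. What the missing intervals would look like**

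Inputs:
- Total of about 320 participants (Section 9.9) and 7 arms (Section 6.3.1). Cohort and arm sizes are redacted. Equal arms would give 320/7 = 45.7, so 40 to 60 per arm is assumed.
- Event rates are assumed: about 20% vs 10% for discontinuation, and about 35% vs 22% for a commoner overall category.
- Method: the unstratified M&N score interval.

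For an observed difference p1 - p2, the 95% limits are the values d that solve

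(p1 - p2 - d) / sqrt(V(d)) = ±1.960, with V(d) = [r1(1 - r1)/n1 + r2(1 - r2)/n2] × N/(N - 1),

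where N = n1 + n2, and r1 and r2 are the maximum-likelihood proportions under the constraint r1 - r2 = d.

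Worked case, 8/40 vs 4/40 (p1 - p2 = 0.100):
- Lower limit d = -0.0622: r1 = 0.1315, r2 = 0.1937, V = 0.006845, and (0.100 + 0.0622)/0.0827 = 1.96.
- Upper limit d = 0.2654: r1 = 0.3300, r2 = 0.0645, V = 0.007125, and (0.100 - 0.2654)/0.0844 = -1.96.

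| Assumed counts | Difference (points) | 95% CI | Half the CI width |
|---|---|---|---|
| 8/40 vs 4/40 | 10.0 | -6.2 to 26.5 | 16.4 |
| 12/60 vs 6/60 | 10.0 | -3.0 to 23.3 | 13.2 |
| 14/40 vs 9/40 | 12.5 | -7.5 to 31.8 | 19.7 |
| 16/46 vs 10/46 | 13.0 | -5.5 to 31.0 | 18.3 |
| 21/60 vs 13/60 | 13.3 | -2.9 to 29.1 | 16.0 |

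Under these assumptions a doubling of the discontinuation rate, from 10% to 20%, is compatible with anything from a small reduction to an excess of more than 20 points.

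**The case against.** The strongest reply is that the comparison is already planned. Tier 2 gives M&N differences with 95% CIs for common AE terms and, at the lower 5% threshold, for Grade 3-5 AEs and SAEs. This stands. A reader might infer from the Tier 3 sentence that the comparative safety objective gets no between-arm estimate at all, and 9.6.2 does not support that. Nor does it support the inference that the colitis and hepatitis foreseen in Section 2.3 would be compared only by eye: these are specific terms, and either one gets a difference and interval once it reaches a Tier 2 threshold.

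Second, the named endpoint is adverse events, not the proportion with any AE. This also stands. Equating the two is an interpretation, and the any-AE rate may lie near its ceiling, where a difference says little. Discontinuation due to an AE is not open to this reply, because it is named in Section 3 and again in Tier 3.

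Third, the Tier 1 text and the body of Table 12 are redacted. Nothing can be concluded about their content. They do not alter the explicit assignment in the visible text.

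Fourth, Tier 2 intervals are only descriptive, and a reader can derive the same interval from per-arm counts and denominators. That is true, and it limits the severity. It does not explain why a named secondary endpoint under a comparative objective should lack the descriptive interval that a common AE term receives. The reason given for the 10% threshold is that rarer events would obscure the overall safety profile. It does not apply to measures that summarise that profile.

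**Conclusion.** The point holds in a limited form. The visible text plans no between-arm difference or interval for discontinuation due to an AE, or for the six overall AE proportions, although the safety objective is comparative. The case is firm for discontinuation, a named secondary endpoint. It is weaker for the overall proportions, which Section 3 does not list singly. The objective as a whole is partly served through Tier 2.

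Severity is minor. No decision rule or error rate in the visible plan depends on these measures. What is lost is a prespecified statement of precision: half the interval width would be about 13 to 20 points in the cases shown. That range rests on assumed arm sizes of 40 to 60 and assumed event rates. The textual finding rests on neither.

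**What to change.** In Section 9.6.2, state that for discontinuation due to an AE and for the overall AE categories (any, drug-related, serious, drug-related serious, Grade 3-5, drug-related Grade 3-5) the difference between each experimental arm and pembrolizumab monotherapy in the same cohort will be reported with an M&N 95% CI. Label these intervals descriptive and unadjusted for multiplicity, as Tier 2 intervals already are. Bring Table 12 into line. In the same edit, say that the Tier 2 rule for Grade 3-5 AEs and SAEs refers to specific terms, if that is the intent.

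The cost is small. There are 7 measures and 5 contrasts (1 in Cohort A, 4 in Cohort B), so at most 7 × 5 = 35 further descriptive intervals, shown as extra columns in existing tables. The method is already in the plan and no new data are needed. If fewer intervals are wanted, discontinuation due to an AE is the one to keep.
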